H0 – Bonding to NCCLs with FBDC-SE (G1) and MM-SE(G4G6) result in similar restorations (aesthetic, functional and biologic) success rates;

H0 – Bonding to NCCLs with FBDC-SE (G1) and MM-SE (G4G6) adhesives result in similar restoration retention rates;

H0 – Bonding to NCCLs with FBDC by SE and enamel etching mode (FBDC-SE-EE; G2) and MM adhesives by Etch-and-Rinse mode (MM-ER; G3G5) result in similar (no significant differences) clinical (aesthetic, functional and biologic) behaviour/performance;

H0 – Bonding to NCCLs with FBDC-SE-EE (G2) and MM-ER (G3G5) result in similar restorations (aesthetic, functional and biologic) success rates;

H0 – Bonding to NCCLs with FBDC-SE-EE (G2) and MM-ER (G3G5) result in similar restoration retention rates;

H0 – Bonding to NCCLs with FBDC (G1G2) or FBU (G3G4), DC adhesives, and ADU (G5G6) light-curing adhesive, with SE or SE-ER/ER modes result in similar (no significant differences) clinical (aesthetic, functional and biologic) behaviour/performance;

H0 – Bonding to NCCLs with FBDC (G1G2) or FBU (G3G4) and ADU (G5G6) lightcuring adhesive, with SE or SE-ER/ER modes result in similar restorations (aesthetic, functional and biologic) success rates;

H0 – Bonding to NCCLs with FBDC (G1G2) or FBU (G3G4) and ADU (G5G6) lightcuring adhesive, with SE or SE-ER/ER modes result in similar restoration retention rates;

H0 - FDI or USPHS criteria evaluation outcomes not differ for the same data, at 24th month follow-up.

2 – POPULATION, MATERIALS AND METHODS

2.1- TRIAL DESIGN

The trial design follows the Consolidated Standards of Reporting Trials (CONSORT) statement (30). Prospective, double blind, clinical trial; randomized allocation of NCCL restorations by six adhesion interventional groups (6 arms) for examination of restorations performance.

Study will take place in University

Dentistry School Clinic. Participants recruitment between November 2015 and April 2016. Restorations estimated to be done until April or May 2016 year.

-

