In this study will be included participants with clinical diagnosis of tooth structure coronal loss and needs for cervical (vestibular surface) restoration without chemical or bacterial origin, called non-carious cervical lesion (NCCL) located in pre-molars/molars (PM/M) teeth, with cavity dimensions defined in the study design. Therefore, restorations can be made in PM or M teeth; a participant can have up to 16 teeth (8PM + 8M) with NCCL. The number of teeth to restore by participant will be of maximum of 6 and a minimum of one NCCL, within this clinical trial. The allocation of the study arms (G1 to G6) to a particular tooth is randomly allocated, with the information available to the operator/principal investigator in sealed envelopes and previously prepared by the investigator-statistics. The allocation of the study arms (G1, G2, G3, G4, G5, G6) to each tooth by participant is performed randomly, but ensuring that the distribution of the groups is not repeated in the same participant. For this purpose, will be organized by the statistical investigator, 210 envelopes with 35 sequences of 6 study arms, where in each order of 6 groups is randomized.

If the patient has more than six teeth that meet the inclusion criteria, the selection of the PM and M teeth to be included in the clinical trial will be conducted randomly by scenarios randomized by the statistical investigator after participation and contact for the effect (not done a priori, since it is necessary 19448 scenarios prior randomization before observing any patient, whereas the possible teeth to be selected for treatment is between 6 and 16 and the teeth to select from 6).

The participant has as cost the academic/scientific fees, as in usual clinical context of Dentistry School Clinic of **Sector Sector** as "restoration of a tooth surface"/ by tooth to restore (One to six teeth), which of course would have to make even not participating in the investigation, as the Dentistry School Clinic fee scale.

The restorations included in this trial will be evaluated for determine clinical performance from baseline to 24th month by the three calibrated examiners. These observation appointments (three, in two years) as part of the clinical trial will be free of charges for participants. Baseline and 24th month data will be statistically analysing, according to this trial purpose and hypothesis.

2.3-STUDY ADHESION ARMS

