One week, before the Restorative procedure (1st appointment): Inform the patient (Written/Verbal- Anexx-1); Patient signature of informed consent; Fulfilment of the project clinical file (patient identification, general clinical summary, oral clinic examination, oral hygiene state; Annex 2); Dental prophylaxis with fluoride toothpaste and water with a nylon brush. Vitality tests (cold and hot) executed with spray *Endo cool* (ethyl chloride) and warm instrument; Pre-operative sensitivity evaluation by applying air for 10 seconds from a dental syringe placed 2 cm from the tooth surface (16); NCCLs cavities will be evaluated according to the degree (1, 2, 3, 4) of sclerotic dentin (32), cavity dimensions (H-height, W-width, and D-depth) in millimetres (mm) and geometry (evaluated by profile photograph, as Angles Acute (A), Severe (S), Obtuse (O) (16);

1st Appointment-Intervention: Initial intra-oral/cavity surface and tooth digital photography; Teeth anaesthesia with 3% mepivacaine (Scandinibsa, Sintra Business Park, Portugal); Operatory field isolation with cotton rolls and retraction floss (Ultradent)._All cavities cleaned with pumice and water in a rubber cup, followed by rinsing and drying. Selection composite colour by shade guide; Adhesive interventions according to G1 to G6 arms assignment. Adhesive systems will be used as SingleDose mode. Composite restorations (AdmiraFusion Universal nano-hybrid composite) with incremental filling technique (two increments maximum), light-cured (LED Unit) with an intensity of 1000mW/cm2, during 40 seconds. Restorations will be finished immediately with diamond disks (OptiDisc® medium 40μm; Kerr) and burns. Polishing performed with diamond-impregnated silicone polishers (Dimanto, Voco, CuxHaven) during 10 seconds._Intra-oral digital photography of the restoration.

2.6-CLINICAL RECALL

Baseline (30 days after restoration), 12th and 24th months Appointments

1 - Intra-oral digital photography of the NCCL restoration;

2- Pos-operative sensitivity evaluation by applying air for 10 seconds from a dental syringe placed 2 cm from the tooth surface (16);

3 – Clinical direct evaluation by 3 calibrated examiners according to FDI (33) (Annex 3) and USPHS (34) (Annex 4);

4°- Data register.

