Study variable definition_- Clinical/direct observation and performance evaluation acceptance by means of FDI (*FDI World Dental Federation - clinical criteria for the evaluation of direct restorations*) (Adapted from (33) (Annex 3) and USPHS (34) (Annex 4).

2.7- DATA AND STATISTICAL ANALISYS PLAN (SAP)

Data statistical analysis and description according to aims of this trial; Specific program for statistical data analysis (IBM(c) SPSS(c) Statistics vs. 22 or later) will be used. The changes in parameters clinical performance (paired comparison analysis) by both, FDI and USPHS criteria will be assessed by McNemar or Wilcoxon tests, for both

primary and secondary outcomes, to determine differences between treatments with regard to aesthetic, functional and biological parameters from baseline to 24th month recall (longitudinal assessment). Differences will be considered to be significant at P<0.05. Whenever 3 groups will be compared at 24 months' recall, a Kruskal Wallis test will be used and upon significant differences detection, then Mann-Whitney tests considering Bonferroni correction will be used for pairwise group comparisons.

Comparison of FDI and USPHS acceptance (success rate) criteria evaluation outcomes for Esthetic, for Functional and for Biological Parameters, at 24th Month Follow-up, were compared using the chi-square test.

If missing data occurs, that is, if dropouts or non-observed due to loss of retention of the restoration, then the paired comparison will consider for the baseline just the restorations existing at the last moment (24 months).

2.8- OBSERVATIONS REGARDING SAMPLE CALCULATION

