	marginal quality or proximal contacts;	5.4.2
	bulk fractures with or without partial	Chip fracture damaging margins
	loss(less than half of the restoration)	5.4.3
		Notable enamel or dentine wall fracture
5. Clinically poor (replacement	4.5. Parcial or complete loss of restoration	5.5
necessary)		Filling is loose but in situ.
Acceptable or not acceptable (n, %, and reasons)	
Adapted from (33)		

c) BIOLOGICAL PROPERTIES	6. Postoperative Hipersesibility, tooth vitality	7. Recurrence of Caries, erosion, abfraction	8. Tooth integrity (enamel cracks)
1. Clinically excellent/ very good	6.1 No hipersensitivity, normal vitality	7.1 No secondary or primary caries	8.1 Complete integrity.
2. Clinically good (after correction, very good)	6.2 Low hipersensitivity for a limited period of time, normal vitality.	7.2 Very small and localized1. Demineralization2. Erosion or3. Abfraction.No operative treatmentrequired	8.2.1 Small margin enamel(<150 μm) 13.2.2 Hairline crack in enamel (<150 μm not probable)
3. Clinically sufficient/ satisfactory (minor shortcomings with no adverse effects but not adjustable without damage to the tooth)	 6.3.1 Premature/slightly more intense 6.3.2 Delayed/weak sensitivity; no subjective complaints, no treatment needed. 	 7.3.Larger areas of 1.Desmineralisation 2.Erosion 3. Abrasion/abfraction in dentine Localized and acessible and can be repaired 	8.3.1 Enamel split(<250 μm) 8.3.2 Crack < 250 μm, no adverse effects.
4. Clinically unsatisfactory (repair for prophylactic reasons)	6.4.1 Premature/very intense 6.4.2 Extremely delayed/weak with subjective complaints 6.4.3 Negative sensitivity intervention necessary but not replacement	7.4.1Caries with cavitation 7.4.2 Erosion in dentine 7.4.3 Abrasion/abfraction in dentine Localized and accessible and can be repaired	 8.4.1 Major enamel split (gap>250 μm or dentine or base exposed) 8.4.2 Crack>250 μm (probe penetrates).
5. Clinically poor (replacement necessary) Acceptable or not acceptable (n, %, and read	6.5 Very intense, acute pulpitis or no vital.Endodontic treatment is necessary and restoration has to be replaced.	7.5 Deep secondary caries or exposed dentine that is not accessible for repair of restoration.	8.5 Cusp or tooth fracture.
Acceptable or not acceptable (n, %, and rea Adapted from (33)	(SUIIS)		

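### FDI and USPHS acceptance are scored on the same restorations, but section 2.7 compares them with a chi-square test that takes no account of the pairing

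*Combined protocol and SAP*

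**What the plan says.** The last null hypothesis under Objectives and Hypothesis is that "FDI or USPHS criteria evaluation outcomes not differ for the same data, at 24th month follow-up". Section 2.6 prescribes, at each recall, "Clinical direct evaluation by 3 calibrated examiners according to FDI (33) (Annex 3) and USPHS (34) (Annex 4". The Annex 2 research file has an FDI grid and a USPHS grid, each with a row per numbered lesion. Annex 3 reduces the FDI scores to "Acceptable or not acceptable".

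For the analysis, section 2.7 describes a "Comparison of FDI and USPHS acceptance (success rate) criteria evaluation outcomes for Esthetic, for Functional and for Biological Parameters", and says that these "at 24th Month Follow-up, were compared using the chi-square test". It does not say which form of chi-square is meant. For change from baseline to 24 months, the same section says that parameters on "FDI and USPHS criteria will be assessed by McNemar or Wilcoxon tests". No paired method is named for FDI against USPHS.

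On clustering, section 2.2 says: "The number of teeth to restore by participant will be of maximum of 6 and a minimum of one NCCL".

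**The concern.** Every restoration supplies one FDI result and one USPHS result, so the comparison is within restoration. The two scales rate overlapping properties (retention, marginal adaptation, sensitivity, caries, colour), and some positive correlation is the natural expectation. A two-sample chi-square counts each restoration twice as if the two ratings came from different teeth, and so misstates the variance of the difference.

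At stake is the answer to the tenth hypothesis. A real difference between the scales may be reported as none. The question is a live one for this trial: the Introduction cites an 18-month study of another universal adhesive in which marginal adaptation differed by FDI but not by USPHS.

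**Working it through.** **Inputs.** From the documents: at least 210 restorations (6 arms × 35, section 2.8); significance at P<0.05 (section 2.7; two-sided assumed); 1 to 6 teeth per participant (section 2.2). Assumed, because the documents give none: failure rates, overlap between scales, clustering, and 20% loss (210 × 0.8 = 168). The plan states no figure for this comparison, so there is none to reproduce.

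**1. Size of the two-sample test.** Let p be the common failure rate and phi the between-scale correlation. The chi-square takes the variance of the difference as 2p(1−p)/N. For paired ratings on independent teeth it is 2p(1−p)(1−phi)/N. The true size is therefore about 2[1−Φ(1.96/√(1−phi))]:

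| phi | Approximation | Exact enumeration, N=210, p=10% |
|---|---|---|
| 0 | 5.0% | 4.9% |
| 0.2 | 2.8% | 2.8% |
| 0.4 | 1.1% | 1.1% |
| 0.6 | 0.2% | 0.2% |

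**2. One worked table: 14 against 7 failures of 210.** Pooled rate 21/420 = 0.05; SE = √(0.05 × 0.95 × 2/210) = 0.02127; z = (7/210)/0.02127 = 1.567; chi-square = 2.456, p=0.117, whatever the overlap. Exact McNemar is 2·P(Bin(b+c, 0.5) ≤ min(b, c)), where b and c count the restorations failing on one scale only:
- 6 fail on both (b=8, c=1): 2 × (1+9)/512 = 0.039; phi = (6×195 − 8×1)/√(14×196×7×203) = 0.59.
- 4 fail on both (b=10, c=3): 2 × (1+13+78+286)/8192 = 0.092; phi = 0.38.

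In this example the verdict at 0.05 changes only at the higher overlap.

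**3. The other form of chi-square.** Run on the FDI-by-USPHS cross-table, the test keeps the pairs, but its null is independence of the two ratings. If the same 14 of 210 fail on both scales, the rates are equal, yet chi-square = 210 and the test rejects. It does not address the stated hypothesis.

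**4. Several teeth per mouth.** I used a latent-normal model with variance shares of 0.3 for participant, 0.2 for error, s for mouth-level disagreement between scales and 0.5−s for tooth. The clustered rule is a participant-clustered McNemar test, with an exact sign-flip p-value if fewer than 10 participants are discordant. Rejection rates are for s = 0 / 0.1 / 0.2.

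| Setting | Two-sample chi-square | Ordinary exact McNemar | Clustered rule |
|---|---|---|---|
| Null, 10% failures, 35 mouths × 6 teeth | 0.5 / 3.8 / 8.2% | 2.7 / 7.4 / 11.2% | 4.2 / 4.7 / 4.5% |
| 10% vs 4% failures, 28 × 6 (N=168) | 61 / 57 / 56% | – | 69 / 52 / 39% |
| 10% vs 4% failures, 84 × 2 (N=168) | 62 / 60 / 61% | – | 80 / 73 / 66% |

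Over 24 null settings (1, 2, 3 or 6 teeth per mouth; 3% or 10% failures; three values of s), the two-sample chi-square exceeded 5% only with six teeth in every mouth and s = 0.2 (8.2% and 7.5%). Elsewhere it rejected 0.4% to 4.5%. The clustered rule rejected 1.1% to 5.4% throughout.

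**The case against.** **The wording may mean McNemar's chi-square.** This is unlikely: section 2.7 names McNemar separately for its paired comparisons, and gives the plain name here.

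**High correlation is not documented.** This stands. The Annex 2 grids differ between scales: FDI aesthetics includes luster where USPHS has marginal discoloration, and FDI biology includes tooth integrity where USPHS has gingival bleeding. Only the functional items nearly match. Correlation may be low in two of the three domains, and the cost is then small.

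**A paired test need not gain power.** This also stands. A reader might infer from ordinary McNemar on independent teeth that the plan gives up a great deal of power: at 10% against 4% failures, N=168 and phi 0.6, exact McNemar has 93% and chi-square 62%. But that test ignores several teeth per mouth, which this plan allows. For a test that respects clustering the gain is smaller, and it reverses in some heavily clustered settings (table in step 4).

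**The cross-table reading is the less natural one.** Agreed. Section 2.7 speaks of comparing success rates, which points to the two-sample form. A reader might cite the cross-table's extreme p-values as the main harm, but the documents do not say that this form was meant. Striking examples can also mislead: with 21 against 7 failures and one restoration failing on both, the cross-table gives p=0.70 and exact McNemar 0.009, but the two-sample chi-square also rejects (p=0.006).

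**The paired data remain recoverable.** True, since Annex 2 records both scales per lesion. That makes the correction cheap, but does not make the named test the right one.

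**Conclusion.** The point holds and should be fixed. The named test does not fit paired ratings on either reading: the two-sample form has the wrong variance, and the cross-table form has the wrong null. In the two-sample form the usual direction is conservative, with true size about 2.8% at phi 0.2 and 0.2% at phi 0.6 (10% failures, N=210, independent teeth), which tilts the result towards no difference. How far this would change the trial's answer cannot be known from the documents, because they give neither failure rates nor overlap.

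Two stronger conclusions are not supported. A reader might infer that the test generally inflates false positives. In the simulations it did so only in the extreme case of six teeth in every mouth with a 20% share of mouth-level disagreement. A reader might also infer that the adhesive comparisons are compromised. The pairing error concerns only the tenth of ten hypotheses, which compares scoring systems. The absence of any allowance for clustering in section 2.7 is a separate gap and matters here only for the choice of replacement test.

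**What to change.** In section 2.7, replace the chi-square sentence with a paired analysis for each of the aesthetic, functional and biological domains:

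1. Report the paired 2×2 table (acceptable or not, FDI by USPHS) and the paired difference in acceptance, with a 95% confidence interval using participant-level (cluster-robust) variance.
2. Test marginal homogeneity with a McNemar test that treats the participant as the cluster. With d_k the FDI-only minus USPHS-only failures in participant k, refer (Σd_k)²/Σd_k² to chi-square on 1 df.
3. State in advance that when few participants are discordant (for example fewer than 10 with non-zero d_k), the p-value is the exact sign-flip version on the d_k, with p=1 if all are zero. The need is real: four participants with d=1, all in one direction, give p=0.046 by the formula in item 2 but 2/2⁴ = 0.125 by sign-flip.
4. State one decision rule for the three domain p-values, for example Holm adjustment, with the overall null rejected if any adjusted p<0.05.
5. Label kappa and ordinary McNemar as descriptive.

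The paragraph should also point to the rule that turns the item scores and the three examiners' scores into one acceptable/not result per restoration and domain. Sections 2.6 and 2.7 do not state it, and the planned chi-square needs it too.

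The cost is one paragraph and no new data. The downsides are slightly more analysis work, possibly a short script for the sign-flip p-value, and a less favourable p-value if disagreement between the scales clusters within mouths.

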ANNEX 4 USPHS (MODIFIED U.S. PUBLIC HEALTH SERVICE) CRITERIA Used for Clinical Evaluation

PARAMETER	CRITERIA	RYGE SCORE*			
ESTHETICS	Surface Staining	Alfa (α): No staining in the restoration and/or the tooth			
Lonnes	Surface Stanning				
		Bravo (B): Slight staining in the restoration and/or the tooth			
		Charlie (χ): The staining penetrated in the restoration and/or the tooth			
	N	in a pulpar direction			
	Marginal	Alfa (α): No discoloration along the margin between the restoration an			
	Discoloration	adjacent tooth			
		Bravo (3): Slight discoloration along the margin between the restoration			
		and the adjacent tooth (removable, usually localized)			
		Charlie (χ): Deep staining cannot be polished away			
	Color Match	Alfa (α)*: Restoration matches the adjacent tooth structure in color and			
		translucency			
		Bravo (3)*: Light mismatch in color, shade or translucency between th			
		restoration and the adjacent tooth			
		Charlie $(\chi)^*$: The mismatch in color and translucency is outside the			
		acceptable range of tooth color and translucency			
FUNCTIONAL	Retention	Alfa (a): Retained			
		Bravo (B): Partially retained			
		Charlie (χ): Missing			
	Marginal Integrity	Alfa (α): No visible evidence of crevice along the margin			
	(Adaptation)	Bravo (B): Visible evidence of a crevice along the margin into which			
		the explorer will penetrate			
		Charlie (χ): Dentin or the base is exposed			
		Delta (δ)*: Restoration is fractured, mobile or missing			
BIOLOGICAL	Postoperative	A: No evidence of postoperative sensitivity			
	Sensitivity	B: Experience of postoperative sensitivity			
	Secondary Caries	A*: No evidence of caries			
		B*: Evidence of caries along the margin of the restoration			
	Gingival Bleeding	A: No evidence of gingival bleeding adjacent to Class II restoration			
		B: Evidence of gingival bleeding adjacent to Class II restoration			
*Alfa (α): Clin	ically excellent/ verv	good; highest degree of clinical acceptance. Bravo (B): Clinical			

present. B: Presence of pathology, related to restoration.

[†]Source: Adapted from (34)

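### Read literally, the missing-data rule removes completely lost restorations from both time points of the paired tests, so the three items that grade complete loss cannot show it there

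*Combined protocol and SAP*

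**What the plan says.** Section 2.7 of the combined protocol and SAP assigns McNemar or Wilcoxon tests to the change from baseline to 24 months in the FDI and USPHS aesthetic, functional and biological parameters. It gives these tests a leading role: they serve "primary and secondary outcomes, to determine differences between treatments", for both criteria sets.

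The last paragraph of that section sets the missing-data rule. It is triggered "if dropouts or non-observed due to loss of retention of the restoration". In that event "the paired comparison will consider for the baseline just the restorations existing at the last moment (24 months"). No exception is made for items on which loss has a grade.

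Elsewhere, loss is something examiners observe. Section 2.6 provides at every recall for "Clinical direct evaluation by 3 calibrated examiners according to FDI" and USPHS. Complete loss has a grade on three items, all in the functional group:

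- FDI item 4, grade 4.5: "Parcial or complete loss of restoration" (Annex 3)
- USPHS Retention, Charlie: the restoration is missing (Annex 4)
- USPHS Marginal Integrity, Delta: "Restoration is fractured, mobile or missing" (Annex 4)

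FDI item 5 does not join this list. Its worst grade is "Filling is loose but in situ", which a lost restoration cannot meet.

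**The concern.** The rule puts two different events in one class. When a participant drops out, the state of the restoration is unknown. When a participant attends and the restoration is gone, the state is known and is the worst grade the scale offers. Removing the second kind of case makes inclusion in the analysis depend on the outcome: failures leave and survivors stay.

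At stake is the longitudinal assessment of function. On the three items, a baseline-to-24-month test that drops every completely lost restoration will report stability however many are lost. The same would hold for functional acceptance if it is tested in pairs. That is an inference: McNemar needs a binary outcome and Annex 3 records acceptable or not acceptable for each property group, but section 2.7 names acceptance only in the 24-month chi-square comparison of FDI with USPHS.

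**Working it through.** **The plan's own figures.** Six arms of 35 give 6 × 35 = 210 restorations, as stated in sections 2.2 and 2.8. The figure of 80 cases for a McNemar comparison in section 2.8 has no stated inputs, so it cannot be checked. Nothing below depends on it.

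**Inputs.** n = 35 per arm (Table 1, section 2.8) and a significance level of 0.05 (section 2.7; two-sided is assumed because the plan does not say).

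**Assumptions.** The test is run within an arm, all 35 restorations are retained at baseline, there is no dropout and there is no change other than complete loss. The number of losses, k, is assumed because the documents give no rate. Pairs within an arm are treated as independent, since section 2.2 does not repeat a group within a participant.

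**Under the rule.** The k lost restorations leave both sides. The table has 35 − k pairs, all retained at both times. There are no discordant pairs and p = 1 for any k.

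**With losses scored.** All k discordant pairs go in one direction.

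- Exact two-sided McNemar: p = 2 × 0.5^k. The exact signed-rank test gives the same value, because all differences are tied and share a sign.
- Asymptotic Wilcoxon, without continuity correction: z = √k, p = 2 × (1 − Φ(√k)).

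| k lost | Paired table under the rule | Retained if scored | Exact p | Asymptotic Wilcoxon p |
|---|---|---|---|---|
| 4 | 31/31 | 31/35 = 88.6% | 0.125 | 0.046 |
| 5 | 30/30 | 30/35 = 85.7% | 0.0625 | 0.025 |
| 6 | 29/29 | 29/35 = 82.9% | 0.031 | 0.014 |
| 8 | 27/27 | 27/35 = 77.1% | 0.008 | 0.005 |
| 10 | 25/25 | 25/35 = 71.4% | 0.002 | 0.002 |

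The smallest k with p < 0.05 is 6 for the exact tests and 4 for the asymptotic Wilcoxon (k = 3 gives 0.083). The plan does not choose between them, so both thresholds are carried forward.

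**Chance of reaching the threshold**, with X ~ Binomial(35, r):

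| Assumed loss risk r | Mean losses, 35r | P(X ≥ 6), exact | P(X ≥ 4), asymptotic Wilcoxon | Under the rule |
|---|---|---|---|---|
| 5% | 1.75 | 0.01 | 0.10 | 0 |
| 10% | 3.5 | 0.13 | 0.47 | 0 |
| 15% | 5.25 | 0.43 | 0.79 | 0 |
| 20% | 7.0 | 0.73 | 0.94 | 0 |

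**The case against.** The best defence is a softer reading. The rule starts only where data are missing, and a lost restoration scored Charlie or 4.5 at recall has been observed on that item. Exclusion would then reach only items that cannot be scored, where it is unavoidable. This may be what was intended. But the trigger names loss of retention outright, and the operative clause keeps only restorations that exist at 24 months. It selects restorations, not items, so the words do not support the softer reading. If it was meant, it should be written.

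A second defence is that the consequence is narrow, and much of this stands. None of the null hypotheses concerns change within an arm: they compare groups, or FDI with USPHS. Partial loss still registers, through USPHS Bravo ("Partially retained") and through FDI 4.5, because the restoration still exists. Lustre, staining, colour and FDI item 5 cannot be graded on a lost restoration, so exclusion is reasonable there.

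Two stronger inferences should be resisted. A reader might conclude that the trial would report 100% retention. The 29/29 above is only the margin of the paired table, and the plan does not say that it is the retention rate. A reader might also conclude that the comparisons between adhesives are biased. The rule speaks only of the paired comparison. It does not bind the Kruskal-Wallis, Mann-Whitney or chi-square tests at 24 months, and the plan does not say how losses enter those tests or the rates.

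**Conclusion.** The concern holds for the paired tests. As written, complete loss contributes no discordant pairs on FDI item 4, USPHS Retention and USPHS Marginal Integrity, whatever the number lost, and the tests on those items are biased toward no change. The same applies to functional acceptance if that is tested in pairs.

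The logical point needs no loss rate. Its size does: from 6 losses in an arm of 35 (exact) or 4 (asymptotic Wilcoxon), a decline that would be significant at 0.05 is reported as none. These counts rest on a within-arm test, full retention at baseline, no dropout and no other change.

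Bias in the between-group retention and success hypotheses is not shown. This should be fixed before analysis, but it does not by itself undermine the trial's group comparisons.

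**What to change.** Replace the missing-data sentence in section 2.7 with the following rules.

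1. Only participant dropout is missing. In a participant recalled at 24 months, a restoration present at baseline and completely lost since is an observed failure. Score it FDI 4.5, USPHS Retention Charlie and USPHS Marginal Integrity Delta, count it not acceptable for functional success, and keep it in the paired tests on those items.
2. Baseline is 30 days after placement (sections 2.1 and 2.6). A restoration lost before then has no retained baseline for the paired test. Count it as a failure in the 24-month retention and success rates, and report it separately.
3. The denominator for the 24-month rates is all restorations of recalled participants, present or lost. Add a sensitivity analysis for dropouts, first with all retained and then with all lost. For example, with 5 assumed dropouts and 6 losses among the 30 recalled, the main result is 24/30 (80.0%), with a range from 24/35 (68.6%) to 29/35 (82.9%).
4. Analyse items with no grade for a lost restoration on retained restorations only. Label these results as conditional on retention, and give the number excluded per arm.
5. State whether exact or asymptotic tests will be used, and whether functional acceptance is tested in pairs.

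Rules 2 and 3 go beyond the paired tests. They settle a denominator that the plan leaves open, so that both analyses treat a lost restoration alike.

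The cost is SAP wording and a little more analysis, with no extra visits or participants. Functional results will look less favourable to the extent that restorations are lost.

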It was assumed that the minimum number of adhesive restorations to be held in each of the six arms (G1 to G6) is 35 (210 restorations). The researchers did not have detailed information that allows the estimation of the sample size based on power analysis (the effect of the expected difference to the end of the time considered for the study). Thus, in principle they assumed the rules of thumb, usually considered in research situations where there is no advance information concerning the performance evaluation of these adhesive medical devices available on the market, using this assay. Moreover, when considering a "simple" analysis comparison using a McNemar test (repeated measures) in six groups would be necessary in total, including at least 80 cases (to restore teeth) in the sample. When considering at least 35 restorations by group, researchers are greatly increasing the minimum number stipulated in the aforementioned technique. In addition, clinical studies previously performed on this issue (between 2004 and 2012) relative to the post-market clinical evaluation performance of adhesive products/use mode in NCCLs, in the context of restorative dentistry field, has enabled to measure a minimum of 30 restorations as viable for determining events in a short/mean-term as the clinical performance evaluation of a similar nature of adhesives.

2.9- GOOD CLINICAL PRACTICE FOR CLINICAL RESEARCH

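### The 80-case McNemar figure in section 2.8 does not show that 35 restorations per arm are enough for the between-arm hypotheses

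*Combined protocol and SAP*

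**What the plan says.** Section 2.8 opens with an admission: "The researchers did not have detailed information that allows the estimation of the sample size based on power analysis". It takes 35 per arm (210 in total) from rules of thumb. It then adds two supports. The first is that a McNemar analysis with repeated measures in six groups "would be necessary in total, including at least 80 cases", so that with 35 per group the "researchers are greatly increasing the minimum number stipulated in the aforementioned technique". The second is that earlier studies of adhesives in these lesions worked with a minimum of 30 restorations.

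The section on objectives and hypotheses lists ten nulls. Three compare G1 with G4G6, three compare G2 with G3G5, and three compare the adhesives (G1G2, G3G4, G5G6). A typical one reads "Bonding to NCCLs with FBDC-SE (G1) and MM-SE (G4G6) adhesives result in similar restoration retention rates". The tenth compares the FDI and USPHS ratings of the same restorations.

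Section 2.7 gives McNemar or Wilcoxon for change from baseline to 24 months, Kruskal-Wallis with Bonferroni-corrected Mann-Whitney tests when three groups are compared, and chi-square for FDI against USPHS. Significance is set at P<0.05.

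**The concern.** The 80 is the only required number that the plan attaches to a named test, and the plan presents 35 per arm as far above it. But it belongs to a paired test of change over time within a restoration. A significant or non-significant change within one arm does not tell us whether two arms differ. The fit is poorest for retention: section 2.7 limits the paired comparison to restorations still present at 24 months, so lost restorations leave that test.

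The nulls are worded as similarity. A reader who has been told that the size greatly exceeds a minimum may take P>0.05 as evidence that the adhesives perform alike, when a difference of 10 points would usually be missed.

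**Working it through.** **Inputs from the documents.** 35 per arm, six arms, 210 restorations; stated McNemar minimum 80 in total; significance level 0.05 (sidedness not stated, two-sided assumed). No rates, discordant proportions or power are given.

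**The plan's own figures.** 80/6 = 13.3 per arm, and 210/80 = 2.63, so the size of the stated increase is arithmetically right. The 80 cannot be reproduced because it has no inputs, and many input sets give it. One example is a single paired test with discordant proportions of 21% and 5%, 80% power and two-sided 0.05: (1.96 + 0.84)² × (0.21 + 0.05) / (0.21 − 0.05)² = 7.85 × 0.26 / 0.0256 = 79.7, rounded up to 80.

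**Reading 1: about 13 per arm.** If all k discordant pairs go one way, the two-sided exact McNemar P is 2 × 0.5^k. For k = 5 this is 0.0625 and for k = 6 it is 0.031, so at least 6 one-way changes are needed: 6/13 = 46% of the arm. With a true one-way change rate c, power is P(Bin(n, c) ≥ 6).

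| n | c = 10% | c = 20% | c for 80% power |
|---|---|---|---|
| 13 | 0.1% | 3% | 54% |
| 35 | 13% | 73% | 22% |
| 80 | 82% | >99% | 10% |

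**Reading 2: one paired test on 80 restorations.** The last row shows that this would be a usable test. But an arm has 35 restorations and a pooled pair has 2 × 35 = 70, both below 80. Three arms together (105) exceed it, but a change-over-time test pooled over the arms being contrasted no longer contrasts them.

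**What 35 per arm gives for the hypotheses.** As worded, and if arms are pooled, the contrasts are 35 vs 70 (G1 vs G4G6; G2 vs G3G5) and 70 vs 70 (between adhesives). Keeping the arms separate gives 35 vs 35. Assumptions: the 24-month rates shown, independent restorations, no dropout, two-sided 0.05. Fisher exact power, by enumerating all outcomes:

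| Contrast | 95% vs 85% | 95% vs 75% |
|---|---|---|
| 35 vs 70 | 24-36% | 75-80% |
| 70 vs 70 | 41% | 91% |
| 70 vs 70 at 0.05/3 | 23% | 81% |
| 35 vs 35 | 14% | 55% |

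The range at 35 vs 70 depends on which side has the lower rate; power is higher when the single arm does.

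Fisher is conservative. The normal approximation for 95% vs 85% gives 30-43% (35 vs 70), 51% (70 vs 70), 33% (70 vs 70 at 0.05/3) and 28% (35 vs 35). The conclusion is the same.

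**Precision at 95% vs 85%.** The 95% CI half-width is 1.96 × √(p1(1−p1)/n1 + p2(1−p2)/n2):

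- 35 vs 35: 1.96 × √(0.0475/35 + 0.1275/35) = 0.139, or 14 points.
- 35 vs 70: 0.129 if the single arm has the lower rate, 0.111 if it has the higher; 11-13 points.
- 70 vs 70: 1.96 × √(0.0475/70 + 0.1275/70) = 0.098, or 10 points.

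**The case against.** The strongest reply is that section 2.8 makes a modest claim. It admits that there was no power analysis, rests first on rules of thumb, and offers McNemar as an additional remark. The increase is claimed only over the minimum for that technique. McNemar is also a planned test: section 2.7 names it for primary and secondary outcomes and describes its purpose as finding differences between treatments, so section 2.8 follows section 2.7. Much of this stands. The mismatch with the hypotheses begins in section 2.7, and the plan does not claim to be powered. But the 80 is still offered as reassurance about size, and no between-group test is sized anywhere in section 2.8.

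A reader might infer three stronger things that the documents do not support:

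- *That the 80 is an arithmetical error.* Its inputs are missing, so it is unverifiable, not refuted. Thirteen per arm is only one reading, and 80 restorations in one paired test would have 82% power at a 10% one-way change rate.
- *That power is as low as the 35 vs 35 row.* Most of the contrasts as worded group the arms, and 35 vs 35 applies only if those groups are split.
- *That 35 per arm is too small.* No target difference is stated, and differences of about 20 points are within reach of most pooled contrasts. The precedent of 30 restorations is a separate argument and is not affected.

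Fisher's test is not one that the SAP names; it serves here as a benchmark for a binary outcome. Clustering of up to six teeth per participant is ignored. Because arms are not repeated within a participant, its effect on power could go either way.

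**Conclusion.** The point holds in this limited form. The 80 is a figure without inputs for a within-restoration test, and it does not support the size for the nine nulls that compare arms. The claim of a large margin fails on both readings: 13 per arm needs nearly half of the restorations to change in one direction, and 80 in one test is more than any arm or pooled pair contains. The tenth null is paired and could use McNemar, but section 2.7 assigns it chi-square.

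On assumed rates of 95% and 85%, power for the contrasts as worded is 24-41% unadjusted and 23% for 70 vs 70 at 0.05/3. At 95% and 75% it is 75-91% unadjusted and 81% for 70 vs 70 at 0.05/3. These figures depend on the assumed rates, independence and no dropout, and any loss to follow-up would lower them. They show what the planned size can and cannot detect; they do not show that the trial needs more restorations.

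**What to change.** In section 2.8:

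1. Delete the 80-case figure and the sentence that calls 35 per group a large increase over it.
2. State that 35 per arm rests on rules of thumb and on earlier studies, which the section already says.
3. Report what 35 per arm delivers for the contrasts as worded (35 vs 70 and 70 vs 70, with 35 vs 35 if arms are kept separate), as power or as expected CI width, with the 24-month rates labelled as assumptions. The figures above can serve.
4. Add that a non-significant result does not by itself show that the adhesives or modes are similar.

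The change is to text only and needs no more participants or restorations. Its cost is that the stated adequacy of the size becomes less favourable.
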